11.2 Randomization

Randomization takes place in 2 groups as balanced randomization by means of a computer-generated random number sequence. This random number sequence is generated with the help of the website www.random.org (numbers, random sequence generator). The first 20 results of this list are assigned to the verum group, the other 20 results are assigned to the placebo group. Upon admission to the study, the patients receive at random one of these numbers which are contained in sealed envelopes on which the numbers 1 to 40 [sic] are written. The randomization envelope is opened by an independent member of the nursing staff – who is not involved in the further treatment of the patient – several minutes prior to the start of surgery. Such member will fill a 50 ml perfusor syringe with either ropivacaine 0.2 % or physiological saline solution. The patients, surgeons as well as the care-taking nursing staff are blinded as regards the content. The deciphering list will only be opened after conclusion of the last follow-up examination.

11.3 Statistical methods

11.3.1 Dependent variables

Primary dependent variable (primary study endpoint)

- Average VPRS (verbal pain rating scale; 0-10) for pain during the first 48 postoperative hours.
- Maximum VPRS (verbal pain rating scale; 0-10) for pain during the first 48 postoperative hours.

Secondary dependent variables (secondary study endpoints)

- Endpoints related to safety during the treatment period: *Occurrence of AEs, ARs and UARs.*
- Endpoints related to the effectiveness: *Patient satisfaction (VRS), clinical outcome (AOFAS forefoot score, ROM GZGG after 6 weeks), maximum and average pain (VPRS) after 1, 2 and 6 weeks, need for rescue pain medication*

11.3.2 Definition of analysis sets

The intent-to-treat population to be analysed includes all randomized patients to whom the trial medication has been given. The statistical analysis of this set decides on the statement statistically significant or not statistically significant. The per protocol population is also analysed, i.e. those patients for whom no major protocol deviations have occurred.

11.3.3 Data analysis

Confirmatory data analysis

The primary dependent variables (average and maximum VRS for pain during the first 48 postoperative hours) shall be analysed in a confirmatory way for two independent samples using a t-test. This shall be done by means of the current version of the software SPSS Statistics (company IBM, Armonk, New York, USA).

Exploratory data analysis

All secondary dependent variables – patient satisfaction (VRS), clinical outcome (AOFAS forefoot score, ROM GZGG after 6 weeks), maximum and average pain (VPRS) after 1, 2 and 6 weeks – shall be analysed in a purely descriptive way by means of using the current version of the software SPSS Statistics (company IBM, Armonk, New York, USA).

12 Reporting

Minutes of the meetings of the different committees are drawn up in order to document the process and development of the study.

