2.1 Primary study aim

The aim of this study is to document the effect of a postsurgical continuous wound infiltration in comparison with standard treatment. The average and maximum postsurgical pain during the first 48 postoperative hours was chosen as primary endpoint, which shall be recorded by means of VRS (verbal rating scale) for pain:

The null hypothesis is as follows: during the first 48 hours, there is no significant difference in postsurgical pain between continuous wound infiltration with Ropinaest® and placebo.

The alternative hypothesis is as follows: during the first 48 hours, there is a significant difference in postsurgical pain between continuous wound infiltration with Ropinaest® and placebo.

The significance level is chosen with $p < 0.05$.

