3.2 Primary endpoint of the study

The average and maximum postsurgical pain during the first 48 postoperative hours was chosen as primary endpoint which shall be recorded by means of VPRS (verbal pain rating scale) for pain.

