5.4 Randomization

Randomization takes place in 2 groups as balanced randomization by means of a computer-generated random number sequence. This random number sequence is generated with the help of the website www.random.org (numbers, random sequence generator). The first 25 results are assigned to the verum group, the other 25 results are assigned to the placebo group. Upon admission to the study, the patients receive at random one of these numbers which are contained in sealed envelopes on which the numbers 1 to 50 are written. The randomization envelope is opened by an independent member of the nursing staff – who is not involved in the further treatment of the patient – several minutes prior to the start of surgery. Such member will fill a 50 ml perfusor syringe with either ropivacaine 0.2 % or physiological saline solution. The patients, surgeons as well as the care-taking nursing staff are blinded as regards the content. The deciphering list will only be opened after conclusion of the last follow-up examination.

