6.9 Premature termination of the clinical trial

The sponsor is entitled to prematurely terminate the study due to relevant medical/administrative causes. The reasons for discontinuing the study are documented in detail. Patients who are still under treatment when the trial is cancelled, have to undergo a final examination which is documented in the CRF. If the investigator has ethical concerns regarding the continuation of the study, this has to be reported to the sponsor immediately.

The sponsor is entitled to terminate the clinical trial prematurely, if

- the patient recruitment rate is insufficient,
- serious problems with the quality of the collected data, which cannot be solved, occur,
- unforeseeable circumstances have occurred in the respective trial center which do not allow for the clinical study to be continued,
- early proof is provided that one treatment group is superior or, respectively, inferior to the other treatment group (determined by interim evaluation),
- unjustifiable risks and toxicities have occurred (decision following renewed risk/benefit assessment),
- new scientific findings, which appear when the study is being carried out, do not allow for the study to be continued.

The head of the study may decide on cancelling the study with the sponsor or the protocol committee.

7 Adverse events, adverse reactions

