11.1 Sample size planning

Statistical planning and analysis takes places under the direction of Mag. [name] of the Institute for experimental orthopaedics.

By using the software G*Power (Franz Faul, University of Kiel, Germany), an a priori sample size analysis is carried out. The following parameters shall be assumed for the calculation of the optimal sample size:

- Primary target variable: average VRS (verbal rating scale; 0-10) for pain
- Clinically-relevant difference: 1
- Number of groups: 2 (same group size)
- Statistical methods:
 - Test family: t-test
 - Statistical test: means; difference between two independent means (groups)
 - Type of power analysis: a priori
- Formulation of hypothesis: two pages
- Effect size: Cohen's $d = 1$ (large effect size)
 - assumed mean difference: 1
 - assumed standard deviation: 1
- Type 1 error: 5 %
- Type 2 error: 20%
- Test power: 80%

- Group size: N1=N2
- Drop-out rate: approx. 10 %

An a priori sample size analysis using the parameters mentioned above, results in a targeted minimal power of 0.80 and with a Cohen's d of 1 (reveals large effects) results in a number of 34 people necessary (17 per group). Considering that the drop-out rate is expected to be at 10 %, the optimal sampling size is 40 feet (20 per group). By means of the sampling size used by us, it should be possible to reveal effects of large size with sufficient power.

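### Average and maximum 48-hour pain are both confirmatory primary variables at a single 0.05 level, with no rule for combining them, so neither the 5% type I error nor the 80% power is assured

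*Combined protocol and SAP*

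**What the plan says.** The Synopsis and sections 2.1, 3.2, 11.3.1 and 11.3.3 all make average and maximum pain over 48 hours primary. Section 3.2 puts it this way: "The average and maximum postsurgical pain during the first 48 postoperative hours was chosen as primary endpoint". Section 11.3.1 lists two primary dependent variables, the second being "Maximum VPRS (verbal pain rating scale; 0-10) for pain during the first 48 postoperative hours". Section 11.3.3 then states: "The primary dependent variables (average and maximum VRS for pain during the first 48 postoperative hours) shall be analysed in a confirmatory way", each by a two-sample t-test.

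Section 2.1 has a single null hypothesis about postsurgical pain, without saying average or maximum, and a single 0.05 level. Section 11.3.2 says of the intent-to-treat set: "The statistical analysis of this set decides on the statement statistically significant or not statistically significant". That names the analysis set that decides, but not the variable.

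The sample size in 11.1 rests on one variable: "Primary target variable: average VRS (verbal rating scale; 0-10) for pain". It assumes a difference of 1, an SD of 1, 5% type I error and 80% power. No difference or SD is given for the maximum.

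On a related point, section 6.9 lets the sponsor stop the trial when an interim evaluation shows superiority or inferiority. Section 11 plans no interim analysis. Section 5.4 says: "The deciphering list will only be opened after conclusion of the last follow-up examination", and 5.8.4 agrees.

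**The concern.** Two confirmatory tests feed one verdict, and the rule that joins them is missing. Two readings are open, and each misses a figure that the plan states.

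- **Either test suffices.** There are two chances of a false positive at 0.05 each, so the overall error exceeds 5% unless the two variables are perfectly correlated.
- **Both tests must succeed.** The error is held, but the power of the joint requirement is below the power of the average alone, which is all that 11.1 computed.

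If one test is significant and the other is not, the plan gives no verdict. Section 12.1 has the investigator carry out the analysis, so the rule could be chosen after the code is opened and the results are known. It cannot be repaired credibly at that stage.

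**Working it through.** **Inputs from the documents.** Two primary variables, each t-tested (11.3.1, 11.3.3); level 0.05 (2.1, 11.1); d = 1/1 = 1 on the average, equal groups, 17 evaluable per arm, 40 patients after about 10% drop-out (11.1); 50 patients (Synopsis, 3.4); scores every 4 hours (6.2), hence 48/4 = 12 per patient. The hypothesis in 11.1 is read as two-sided.

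**Assumed, because the documents give nothing.** The correlation between average and maximum, the standardised effect on the maximum, and the model for the individual scores.

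**1. The plan's own figure.** For a two-sample t-test, the noncentrality is d·√(n/2) on 2n − 2 degrees of freedom. With n = 17 this is √8.5 = 2.915 on 32 df, the critical value is 2.037, and power is 0.807. With n = 16 power is 0.781. The 17 per arm is reproduced, for the average alone.

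**2. Either test suffices.** Under no effect on either variable, P(either) = 0.05 + 0.05 − P(both). From the bivariate normal distribution:

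| Correlation | P(both) | P(either) |
|---|---|---|
| 0 | 0.0025 | 0.0975 |
| 0.5 | 0.0093 | 0.0907 |
| 0.7 | 0.0165 | 0.0835 |
| 0.8 | 0.0219 | 0.0781 |
| 0.9 | 0.0296 | 0.0704 |

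To see which correlations are plausible, 20,000 null trials were simulated with 25 per arm and 12 scores per patient. Scores were normal with mean 3 and SD 2, rounded and clipped to 0-10. Within-patient correlation was compound symmetry 0.3, 0.5 or 0.7, or AR(1) 0.5, 0.7 or 0.85. The correlation between average and maximum came out at 0.71-0.94, the either-wins error at 6.3-8.3%, and the both-required error at 1.7-3.2%.

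**3. Both tests must succeed.** A false joint claim needs at least one true null to be rejected at 0.05, so the error cannot exceed 5%. Power was simulated with d = 1 on the average; each range covers correlations 0.7 to 0.9. The 22 per arm is 50 patients less 10%: 25 × 0.9 = 22.5, rounded down.

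| d on maximum | 17 per arm | 22 per arm |
|---|---|---|
| 1 | 72-75% | 84-87% |
| 0.8 | 58-61% | 71-73% |
| 0.6 | 38-40% | 49-50% |

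**4. The two tests disagree.** P(disagree) = P(average significant) + P(maximum significant) − 2·P(both). Over the same grid this is 10-44% at 17 per arm and 6-42% at 22. For example, at 17 per arm with d = 0.6 on the maximum and correlation 0.7: 0.807 + 0.396 − 2 × 0.382 = 0.44.

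**5. Candidate repairs.**
- Average first at 0.05, maximum at 0.05 only afterwards. If the null for the average is true, any false claim requires a rejection at that first step, which has probability 0.05. If it is false, the only possible error is on the maximum, again at most 0.05. Power for the average stays at 0.807 with 17 per arm and 0.900 with 22.
- 0.025 for each variable. The error is at most 0.025 + 0.025 = 0.05. Power for the average at 0.025 is 71.2% with 17 per arm, 74.1% with 18 (20 × 0.9) and 83.5% with 22.

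**The case against.** The best counter-argument is that the plan leans towards an answer. Section 11.1 names one target variable, the average, and it is the only one with a difference, an SD and a power. Section 3.2 joins average and maximum as a single endpoint. An average-led or both-required reading is therefore more natural than either-wins, and the error inflation belongs only to either-wins. This does not settle the matter. The average is singled out only as a sample-size input, while the sections that govern the analysis list two primary variables and test both confirmatorily.

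Four further points are fair:

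- The two losses never occur together. Either-wins raises the error but not the risk of missing an effect; both-required does the reverse.
- The largest power losses need d = 0.6 or 0.8 on the maximum, which no section supports or excludes. With d = 1 on both, disagreement at 17 per arm is 10-18%.
- With 22 per arm and d = 1 on both, both-required power is above 80%. That d on the maximum is equally unsupported, and 11.1 and 11.2 still plan 40 patients where 3.4 and 5.4 plan 50.
- For the 0.025 split, the chance that at least one test succeeds is higher than the power for the average alone: 71-82% at 17 per arm and 83.5-91% at 22, over the same grid. The figures in step 5 are therefore the floor for that option.

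The stopping ground in 6.9 is a separate and lesser matter. No look is scheduled, and the conclusion does not depend on it.

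**Conclusion.** The concern holds, and the plan must be changed before unblinding. As written, the trial's only confirmatory verdict has no defined rule. If either test can win, type I error is about 7-10% instead of 5%; for positively correlated scores such as those simulated, 6-8% is the likelier range. If both must win, the stated 80% is missed at the stated 17 per arm: 72-75% at best over correlations 0.7-0.9, and lower if the effect on the maximum is smaller than that on the average.

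That the rule is missing, and that either-wins exceeds 5% at any correlation below 1, needs no assumption. The exact percentages rest on the assumed correlations, the assumed effect on the maximum and, for the 6.3-8.3% range, the assumed score model. No figure is claimed for the interim clause.

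**What to change.** **Primary endpoint.** In the Synopsis, 2.1, 3.2, 11.3.1 and 11.3.3, state that the primary endpoint is average VPRS over the first 48 postoperative hours, tested two-sided at 0.05, and that maximum VPRS over 48 hours is tested two-sided at 0.05 only if the average is significant. Reword the null and alternative hypotheses in 2.1 to match. In 11.3.2, state that the verdict rests on average VPRS. In 11.3.3, exempt the 48-hour maximum from the sentence that makes secondary variables purely descriptive. Add it to the secondary lists in the Synopsis, 2.2, 3.3 and 11.3.1.

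If the sponsor wants either variable to be able to win, 0.025 for each also controls the error, at the loss of power for the average shown above.

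**Interim clause.** Reconcile 6.9 with 5.4, 5.8.4 and section 11. Either remove the interim-evaluation ground, or pre-specify the look, its error control and who runs it unblinded. Section 7.4 already mentions a Data Safety Monitoring Board.

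**Cost.** No extra patients. It takes a written, reasoned and signed change under section 14, and the registered primary outcome (12.2) must match. Maximum pain can no longer carry the claim alone. Removing the ground in 6.9 gives up both the superiority and the inferiority stop; keeping it requires a planned look and an unblinded reviewer.

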5.5 Treatment scheme

5.5.1 Administration instructions

At the end of every patient's surgery, a pain catheter (InfiltraLong Katheter 19G x 420mm, Pajunk Medizintechnologie GmbH) is placed in the surgical wound through which ropivacaine 0.2 % (verum) or NaCl 0.9 % (placebo) is continuously administered at a rate of 2 ml/h during the first 24 postsurgical hours via a syringe pump. The catheter is removed on the following day in the course of the routine change of dressing.

As for standard pain treatment (Non Investigational Medicinal Product, NIMP), the patients receive naproxen 500 mg (Naprobene®, ratiopharm Arzneimittel Vertriebs-GmbH, Wien, Austria) p.o. in the morning and in the evening from day 1 to 8 as well as hydromorphone 2.6 mg (Hydal®, Mundipharma Ges.m.b.H., Austria) p.o. in case of VRS > 3 (every 4 hours at maximum) from day 1 to 3.

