5.8.4 Regular unblinding

Regular unblinding only takes place after conclusion of the last follow-up examination including documentation.

6 Course of study

See also visit plan. On the day of hospitalization (visit 1, baseline, day 0) for hallux valgus surgery, the measures mentioned under point 6.1 are carried out as part of informing the patient on the surgery. On day 1, hallux valgus surgery is performed under local anaesthesia, at the end of the surgery the pain catheter (InfiltraLong-Katheter 19G x 420mm, Pajunk Medizintechnologie GmbH) is inserted to allow for continuous wound infiltration with ropivacaine 0.2 % or with physiological saline solution. After surgery, the care-taking nursing staff of the respective ward documents the pain level under continuous wound infiltration and standard pain treatment every 4 hours via VRS (visit 2, see point 6.2). On day 2 (first postsurgical day), the pain catheter is removed in the course of the first routine change of dressing during morning visit (approx. 07.30 a.m.). Under standard pain treatment, the care-taking nursing staff continues to document the pain level every 4 hours via VPRS. On day 3 (second postsurgical day), the patient is discharged from hospital. He/she receives a prescription for the intended pain medication as well as further follow-up appointments in 1 (visit 3), 2 (visit 4) and 6 weeks (visit 5). In the course of these outpatient postsurgical follow-ups, the examinations described under points 6.3 to 6.5 are carried out and AEs and SAEs are recorded. Visit 5 (outpatient 6 weeks follow-up) represents the end of the study's follow-up period. After conclusion of the study, the examining doctor decides on further outpatient follow-ups.

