6.1 Visit 1 (baseline, day 0)

Prior to admission to the clinical trial, every patient must be informed in detail on the study. Information takes place in person by the treating doctor and in writing by means of the patient information. Only after all questions of the patient have been answered, he/she will be asked to sign two copies of the declaration of consent and to personally date it. Following this, the patient receives a copy of the patient information/declaration of consent; the second copy is kept in the investigator site file.

Upon visit 1, demographic data (age, sex, weight, size, BMI, side) is recorded. Furthermore, physical examination is carried out, including examination of the range of motion (ROM) of the hallux metatarsophalangeal joint (GZGG) as well as assessment of AOFAS forefoot score by means of the "AOFAS Hallux Metatarsophalangeal-Interphalangeal Scale" questionnaire and the average and maximum VPRS. Women of childbearing age undergo laboratory testing to exclude pregnancy. After final examination of the inclusion and exclusion criteria, the patient is admitted to the study, including his admission to one of the two treatment groups according to randomization as explained above.

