6.6.1 Assessment of effectiveness

Effectiveness is assessed by the care-taking nursing staff – which is blinded as regards the therapy group – collecting data concerning the VPRS for pain during the patient's stay in hospital which is repeated every 4 hours. For this, the patient indicates the current pain level on a scale ranging from 0 - 10 (0 meaning no pain, 10 meaning the maximum pain imaginable).

Before surgery and in the course of the postsurgical outpatient follow-ups, the respective care-taking doctor assesses not only the pain level by means of VPRS for pain but also the ROM of the hallux metatarsophalangeal joint. Furthermore, upon visit 1 and 5, AOFAS forefoot score is assessed by means of the „AOFAS Hallux Metatarsophalangeal-Interphalangeal Scale“ question-

naire (see annex) and patient satisfaction is assessed by means of VRS.

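### The confirmatory t-test is valid but leaves the visit 1 VPRS unused; a pre-specified ANCOVA is a cheap, optional gain if |r| exceeds about 0.15 to 0.18

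*Combined protocol and SAP*

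**What the plan says.** All references are to the combined protocol and SAP.

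- **Test.** Under section 11.3.3, the average and maximum pain scores over the first 48 postoperative hours "shall be analysed in a confirmatory way for two independent samples using a t-test". No covariate is named there or elsewhere in section 11.
- **Baseline.** Section 6.1 lists among the visit 1 assessments the AOFAS "questionnaire and the average and maximum VPRS". The visit plan also ticks a pain score at baseline. Section 6.6.1 confirms that before surgery "the respective care-taking doctor assesses not only the pain level by means of VPRS", along with joint motion. Section 11.3.1 lists outcomes only, so the visit 1 score has no stated use.
- **Sample size.** Section 11.1 uses an unadjusted comparison of two means for the average score: difference 1, SD 1, 5% type 1 error, 80% power. The result is 17 per group, raised to 20 for about 10% drop-out. Sections 3.4 and 5.4 give 25 per group.
- **Analysis set.** The intent-to-treat set in section 11.3.2 "includes all randomized patients to whom the trial medication has been given".
- **Pain treatment.** Section 5.5.1 allows hydromorphone "p.o. in case of VRS > 3 (every 4 hours at maximum) from day 1 to 3". The trial infusion is "continuously administered at a rate of 2 ml/h during the first 24 postsurgical hours via a syringe pump".

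**The concern.** Each of the two primary variables has a preoperative counterpart that is collected and then ignored. Visit 1 precedes surgery, and section 5.4 has the randomization envelope opened only minutes before surgery. The score therefore cannot be affected by treatment and is a legitimate covariate. If preoperative pain predicts postoperative pain, the unadjusted test gives up precision that costs nothing to recover, in a trial of only 40 to 50 patients.

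Whether it does predict is unknown. Visit 1 pain is pain from the deformity, while the outcome is acute surgical pain with an opioid available above a score of 3, which may compress differences between patients. The correlation may be low, and adjusting for an uninformative covariate carries a small cost.

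**Working it through.** **Inputs.** Difference 1, SD 1, alpha 0.05 and target power 0.80 come from section 11.1. The wording on sidedness there is garbled in translation and is read as two-sided. Group sizes are 17 (section 11.1, evaluable), 20 (11.1), 25 (3.4), 18 (20 less 10%) and 22 (25 less about 10%). Every value of r is an assumption.

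**Step 1: the plan's own figure.** t-test power comes from the noncentral t with df = 2n - 2 and noncentrality d × sqrt(n/2). For n = 17 the noncentrality is sqrt(8.5) = 2.915 and power is 0.807. For n = 16 power is 0.781. So 17 per group (34 in total) is reproduced. A one-sided test would need only 14 per group, which supports the two-sided reading.

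**Step 2: break-even on variance.** With N = 2n and one random baseline covariate, the variance of the ANCOVA estimate relative to the unadjusted difference is (1 - r²)(N - 3)/(N - 4). Setting this to 1 gives |r| = 1/sqrt(N - 3):

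- N = 34: 1/sqrt(31) = 0.180
- N = 40: 1/sqrt(37) = 0.164
- N = 50: 1/sqrt(47) = 0.146

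**Step 3: power.** ANCOVA has df = 2n - 3 and noncentrality d × sqrt(n/2) / sqrt((1 - r²)(1 + T²/(2n - 2))), averaged over the chance baseline imbalance T, which follows a t distribution on 2n - 2 df. Results for the average score at d = 1:

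| Per arm | t-test | r = 0 | r = 0.1 | r = 0.2 | r = 0.3 | r = 0.5 | Break-even r |
|---|---|---|---|---|---|---|---|
| 17 | 0.8070 | 0.7936 | 0.7976 | 0.8095 | 0.8296 | 0.8938 | 0.184 |
| 18 | 0.8300 | 0.8180 | 0.8218 | 0.8331 | 0.8521 | 0.9114 | 0.178 |
| 20 | 0.8690 | 0.8593 | 0.8627 | 0.8728 | 0.8894 | 0.9389 | 0.169 |
| 22 | 0.8997 | 0.8921 | 0.8951 | 0.9038 | 0.9180 | 0.9583 | 0.161 |
| 25 | 0.9337 | 0.9285 | 0.9308 | 0.9376 | 0.9484 | 0.9769 | 0.150 |

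Change in power, in percentage points, at r = 0 / 0.2 / 0.3 / 0.5:

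- 17 per arm: -1.3 / +0.3 / +2.3 / +8.7
- 25 per arm: -0.5 / +0.4 / +1.5 / +4.3 (the third entry is 0.9484 - 0.9337 = 0.0147; it reads 1.4 if the powers are first rounded to three decimals)

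**Step 4: the same in patients.** Per-arm n for 80% power is 17 with the t-test. With ANCOVA it is 18 (r = 0 or 0.1), 17 (0.2), 16 (0.3) and 14 (0.5).

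**Step 5: simulation check.** With 40,000 normal-data trials per setting, 17 per arm gave ANCOVA 0.796 against t-test 0.809 at r = 0, and 0.828 against 0.805 at r = 0.3. At 25 per arm and r = 0.3 it gave 0.948 against 0.932. In a separate simulation of 60,000 trials per setting, type I error was 0.049 to 0.051 for both tests.

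**The case against.** The strongest reply is that nothing is broken. Section 11.3.3 fixes one test and section 11.1 sizes the trial for it. That stands, and it is why this is optional.

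A second reply is that with r unknown and plausibly low, ANCOVA should not be the default. In part this stands. At r = 0.2 the gain is under half a point, and at 17 per arm r = 0 or 0.1 leaves power just under 80% (0.794 or 0.798). The larger gains need r of 0.3 to 0.5. Against this, the loss is capped at 1.3 points while the possible gain is several times larger, and the t-test remains the fallback if the sponsor has evidence of a low r.

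A third reply is that the covariate is loosely defined. Section 6.1 gives no recall period for the visit 1 average and maximum, whereas section 6.6.1 defines the in-hospital score as pain at that moment, taken every 4 hours. Pairing average with average matches labels, not demonstrably the same measure. This stands. It affects how large r may be, not the validity of the adjustment, and the recall period should be stated. The powers also cover the average only, because section 11.1 gives no SD for the maximum.

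Three stronger readings are not supported:

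- A reader might infer that the t-test is wrong. It is valid under randomization.
- A reader might infer that the plan leaves room to choose between adjusted and unadjusted results. As written, it offers no adjusted result. The need to fix the choice before unblinding arises only if ANCOVA is added.
- A reader might infer that the trial is underpowered because the infusion covers 24 of the 48 hours: (24 × 1 + 24 × 0)/48 = 0.5 point, with power 0.34 at 20 and 0.41 at 25 per arm. These figures are illustrations only. Section 11.1 does not tie its 1-point difference to the infusion hours, and nothing says the effect is zero afterwards.

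**Conclusion.** The point holds as an optional, low-cost improvement. The confirmatory test is sound, but it sets aside a preoperative score already collected for both primary variables. Adjustment improves power for the average once |r| exceeds about 0.18 at 17 per arm or 0.15 at 25 per arm, and loses at most 1.3 points (17 per arm, r = 0) otherwise. The size of the gain cannot be known from the documents. It rests on assumed r, on the plan's d = 1, and on approximately normal scores. The conflict between 40 and 50 patients is a separate matter and only moves the threshold between about 0.17 and 0.15.

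**What to change.** 1. **Before unblinding, in section 11.3.3:** name ANCOVA on treatment plus the matching visit 1 VPRS (average for average, maximum for maximum) as the confirmatory analysis, with the unadjusted t-test as a sensitivity analysis. State the recall period of the visit 1 score. State a rule for a missing visit 1 score that keeps every patient in the intent-to-treat set of section 11.3.2. If the sponsor has data placing |r| below break-even, keep the t-test as confirmatory and list ANCOVA as the sensitivity analysis.
2. **Optional addition:** keep 0-48 hours as the primary window and pre-specify supportive 0-24 and 24-48 hour summaries from the planned 4-hourly readings, as far as these exist before discharge on day 3. They spend no alpha.
3. **To be handled as a separate point:** the 24-hour infusion (synopsis, section 5.5.1) and catheter removal at about 07:30 on day 2 (sections 6 and 6.2) need to be reconciled. Until then a split at 24 hours does not cleanly separate hours with and without infusion.

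The cost is a few sentences, plus the written, reasoned and signed amendment that section 14 requires. Items 1 and 2 need no new measurements, no more patients and no change of endpoint. The statistical downside of item 1 is the small power loss if |r| is below break-even: at r = 0, 0.807 falls to 0.794 at 17 per arm, while 18 per arm (20 less 10%) still has 0.818.
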